### **Visit 1 (Screening visit, WRNMMC or NIH CC)**

Prospective, eligible participants with documented systolic heart failure meeting study inclusion criteria will undergo a screening visit. All screening tests will be performed only after obtaining consent.

#### **The following procedures will be performed at the screening visit:**

- Demographic information, medical history, physical examination, current medical treatments will be reviewed
- Blood draws will analyze: CBC+Diff, BNP, HbA1C, uric acid, ALT, CK, Chemistry panel (electrolytes, glucose, blood urea nitrogen and creatinine) and insulin levels.
- Urine pregnancy test at screening in women of child-bearing age  
Baseline echocardiogram (optional at Visit 1 if PI feels there is an adequate and timely historical echo)

If eligible, consent to protocol

\* Blood draw not required at screening visit for patients who have historical blood work (within the last 6 months from the time of consent).

If enrollment takes place at WRNMMC, the signed consent form will then be faxed to the NHLBI Investigator team and subjects will be remotely registered at the NIH Clinical Center (Off-site registration) to obtain an NIH CC medical record number.

### **Visit 2 (Week 0, NIH)**

#### **The following procedures will be performed at Visit 2:**

- Brief history to review heart failure symptoms
- NIH consent
- Blood draws will analyze: CBC+Diff, BNP, HbA1C, uric acid, ALT, CK, Chemistry panel (electrolytes, glucose, blood urea nitrogen and creatinine) and insulin levels. This blood draw will not be performed if subject has normal clinical blood work within the last two weeks.
- Baseline skeletal muscle exercise NMR Spectroscopy
- Urine pregnancy test for women with childbearing potential
- Skin biopsy will be done at Visit 2 or Visit 3

### **Visit 3 (Week 0 + 1-2 days, NIH CC)**

#### **The following procedures will be performed at Visit 3:**

- Dispense NR: Level 1 ( 250mg PO BID to initiate supplementation in evening after visit 3).
- Dispense Level 2-4 bottles of NR: Level 2 (500mg PO BID – to initiate after visit 4), Level 3 (750mg PO BID – to initiate after visit 5) and Level 4 (1000mg PO BID – to initiate after visit 6 and maintain through visit 7).

#### **The following procedures will be performed at either Visit 2 or Visit 3:**

- Baseline Cardio-Pulmonary Exercise Testing
- Research Bloods
- Skin biopsy
- Blood draws will analyze: CBC+Diff, proBNP, HbA1C, uric acid, ALT, CK, Chemistry panel (electrolytes, glucose, blood urea nitrogen and creatinine) and insulin levels. This blood draw is not required if subject has normal clinical blood work within the last three weeks.
- Baseline skeletal muscle exercise NMR Spectroscopy
- Urine pregnancy test for women with childbearing potential

### **Visit 4 (Week 2, WRNMMC or NIH CC)**

#### **The following procedures will be performed at the follow-up visits (Day 14±3):**

- Medical history, physical examination, current medical treatments
- Blood draws will analyze: CBC+Diff, proBNP, HbA1C, uric acid, ALT, CK, Chemistry panel (electrolytes, glucose, blood urea nitrogen and creatinine) and insulin levels
- Record of adverse events, if any
- Study drug adherence with pill count and collect Level 1 NR 250mg PO BID bottle.
- Record of concomitant medications or interventions, if any
- Communicate the initiation of Level 2 NR 500mg PO BID in evening after visit 4

## **Visit 5 (Week 4, WRNMMC or NIH CC)**

**The following procedures will be performed at the follow-up visits (Day 28±3):**

- Medical history, physical examination, current medical treatments
- Blood draws will analyze: CBC+Diff, proBNP, HbA1C, uric acid, ALT, CK, Chemistry panel (electrolytes, glucose, blood urea nitrogen and creatinine) and insulin levels.
- Record of adverse events, if any
- Study drug adherence with pill count and collect Level 2 NR 500mg PO BID bottle
- Record of concomitant medications or interventions, if any
- Communicate the initiation of Level 3 NR 750mg PO BID in evening after visit 5

## **Visit 6 (Week 6, WRNMMC or NIH CC)**

**The following procedures will be performed at the follow-up visits (Day 42±5):**

- Medical history, physical examination, current medical treatments
- Blood draws will analyze: CBC+Diff, BNP, HbA1C, uric acid, ALT, CK, Chemistry panel (electrolytes, glucose, blood urea nitrogen and creatinine) and insulin levels.
- Record of adverse events, if any
- Study drug adherence with pill count and collect Level 3 NR 750mg PO BID bottle
- Record of concomitant medications or interventions, if any
- Communicate the initiation of Level 4 NR 1000mg PO BID in evening after visit 6

## **Visit 7 (Week 12, WRNMMC and/or NIH CC)**

**The following procedures will be performed at the follow-up visit (Day 84 ± 5):**

- 7A WRNMMC (Day 84 +/-5) Medical history, physical examination, current medical treatments
- Blood draws will analyze: CBC+Diff, proBNP, HbA1C, uric acid, ALT, CK, Chemistry panel (electrolytes, glucose, blood urea nitrogen and creatinine) and insulin levels.
- Record of adverse events, if any
- Study drug adherence with pill count
- Record of concomitant medications or interventions, if any
- Continue Level 4 NR - 1000mg PO BID
- Echocardiography

7B NIH (Day 84+/-5)

- Pregnancy test on women with childbearing potential (may be performed at Visit 7 or 8)

- Skeletal muscle exercise NMR spectroscopy or CPET
- Research blood if CPET performed at this visit

### **Visit 8 (Visit 7B + 1-3 days, NIH CC)**

- CPET or Skeletal muscle exercise NMR spectroscopy (whichever was not done at Visit 7B)
- Research blood if CPET performed at this visit
- Pregnancy test on women with childbearing potential (may be performed at Visit 7 or 8)
- Record of adverse events, if any
- Study drug adherence with pill count
- Discontinue NR
- Record of concomitant medications or interventions, if any

### **Visit 9 (Week 16 ± 1 week, NIH)**

The following procedures will be performed at the final study visit (Day 112 ± 5)

- Medical history, physical examination, current medical treatments
- Blood draws will analyze: CBC+Diff, proBNP, HbA1C, uric acid, ALT, CK, Chemistry panel (electrolytes, glucose, blood urea nitrogen and creatinine) and insulin levels.
- Pregnancy test on women with childbearing potential
- Record of adverse events, if any
- Record of concomitant medications or interventions, if any
- Skeletal muscle exercise NMR spectroscopy

#### **Dispensing of dietary supplement:**

The dietary supplement will be stored and dispensed of by the NIH pharmacy.

#### **Description of Study Population and Recruitment**

The WRNMMC has an active heart failure clinic where approximately 500 ambulatory heart failure patients are seen on a regular basis. The Cardiologists staffing the clinic review all heart failure patients the day prior to their appointments and they determine who potentially meets inclusion and exclusion criteria for studies. The patients who are eligible are then informed about the study at their appointments and asked whether they would be willing to be screened, consented and enroll in the studies.

We will also recruit subjects through NIH using traditional recruitment methods such as referrals from other protocols, outside physician referral and self-referral.

The study may also opt to use the following strategies for recruitment of patients :

- ClinicalTrials.gov
- Clinical Center Research Studies website
- National Heart, Lung and Blood Institute (NHLBI) patient recruitment website
- Twitter messages and chats with study investigators
- Social Media posts
- Use of CC Office of Patient Recruitment services including creation and distribution of study flyers and information through pre-existing recruitment avenues such as the NIH recruitment listserv.

Up to 25 participants may be recruited for this study with the objective of having 15 subjects completing the study.

#### **4. Eligibility Assessment**

The PI and/or AI at WRNMMC or NIH will assess eligibility. Screening will be performed under this protocol only. Screening studies for subject enrollment:

- i. History and physical examination.
- ii. Screening and Research laboratory tests may include:
  - Acute Care Panel (Na, K, Cl, CO2, Creatinine, Glucose, and Urea Nitrogen)
  - Mineral Panel (Phosphorus, Magnesium, Albumin, and Calcium)
  - Hepatic Panel (Alk Phosphatase, ALT, AST, Total Bilirubin, and Direct Bilirubin)
  - CBC + Differential
  - Insulin level
  - βHCG (females of childbearing potential)
  - proBNP
  - Echocardiogram

### **Eligibility**

#### **Inclusion criteria**

- Men and women between the ages of 18 and 75 years with NYHA Class II-III systolic heart failure (LVEF by standard echocardiography or radionuclide ventriculography of  $\leq 45\%$ ) deemed to be non-ischemic or ischemic in origin.
- Clinically stable (no cardiac procedures or hospitalizations for hospitalizations for cardiac causes, including HF, ischemia or arrhythmia) within the previous 3 months
- Ability to undergo study procedures, including scheduled visits, blood draws, skeletal muscle exercise NMR spectroscopy and CPET testing
- Willingness/ability to provide informed consent
- Must be DEERS eligible to be enrolled in a research protocol at WRNMMC

## Exclusion Criteria

- Heart failure with preserved ejection fraction (LVEF >45%)
- Change in heart failure medications due to deterioration of function with the exception of up- or down-titration of diuretic dose up to 100% of baseline dose.
- Heart failure due to etiologies other than non-ischemic or ischemic. Examples of exclusionary heart failure etiologies include primary valvular disease, or infiltrative or inflammatory cardiomyopathies.
- Cardiac surgery, percutaneous coronary intervention (PCI) or cardiac device implantation within the previous 3 months
- Hospitalizations for cardiovascular causes, including heart failure, chest pain, stroke/TIA or arrhythmias within the previous 3 months
- Inability to perform Study visits or procedures (e.g., physical inability to perform exercise testing)
- Unwillingness/inability to provide informed consent
- ALT > x3 upper limit of normal, hepatic insufficiency or active liver disease
- Recent history of acute gout
- Chronic renal insufficiency with creatinine > 2.5mg/dl
- Pregnant (or likely to become pregnant) women
- Significant co-morbidity likely to cause death in the 6 month follow-up period
- Significant active history of substance abuse within the previous 5 years
- Current participation in another drug study
- History of intolerance to NR precursor compounds, including niacin or nicotinamide
- MRI incompatible hardware including pacemakers or ICD's
- Study adherence concerns
- Individuals with diabetes type 1 and 2 who use insulin
- Women of child-bearing potential unwilling to use contraception or unwilling to practice abstinence
- Breastfeeding women unwilling to stop breastfeeding

## 5. Procedures

### Skeletal muscle exercise NMR spectroscopy (primary outcome):

To measure whether NR enhances mitochondrial function in skeletal muscle NMR spectroscopy will be performed at baseline, at the end of the 12-week ( $\pm$  5-days) NR supplementation period and repeated 4 weeks ( $\pm$  5-days) post-NR washout, using a protocol developed at the NIH. Here, a foot-exercise apparatus is employed to deplete phosphocreatine levels in the tibialis anterior, a muscle in the superficial anterior lateral aspect of the leg mainly composed mitochondrial enriched oxidative type I and type IIA fibers. Each participant engages in submaximal exercise by dorsiflexing one foot against 30% of the maximum weight lifted before testing. The phosphocreatine level will be measured using  $^{31}\text{PMRS}$  during a 3-minute rest period, a 2-minute exercise period, and a 6-minute recovery period, from which the single exponential

recovery time constant ( $T_c$ ) is calculated with data obtained during the post-exercise recovery period. In accordance with the protocol,  $^{31}\text{P}$  spectra will be obtained at rest and during exercise and recovery, and the results will be analyzed with the use of SAGE 7 (GE Healthcare) and IDL, version 6.4 (Exelis Visual Information Solutions), software.

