### 3. Study Design and Procedures

The study design is an open label pilot study with subjects serving as their own controls. The outline of the clinical protocol is shown in a tabular schematic below.

Visit #	1	2	3	4	5	6	7A/B	8	9
Weeks	-1 to -3	0	0+ 1-2 days	2	4	6	12	12 + 1-2 days	16
Procedures									
History	X	X		X	X	X	X		X
Physical exam	X			X	X	X	X		X
Initiate NR/dispense meds			X						
Dose adjustment				X 	X 	X 			
Stop NR								X	
Urine pregnancy test	X 	X 	X 				X 	X 	X 
Clinical blood tests	(X)	X 	X 	X	X	X	X 	X 	X
NMR spectroscopy		X 	X 				X 	X 	X
CPET		X 	X 				X 	X 	
Echo	X*						X		
Research blood		X 	X 					X 	
Skin biopsy		X 	X 						
AE assessment				X	X	X	X	X	X
Concomitant meds/tx	X			X	X	X	X	X	X
Study drug adherence				X	X	X	X		
Key:									
(X) Performed only if baseline laboratory studies not performed during routine testing within 6 months									
X Procedure performed									
 Increase NR dose by 250mg BID									
 Pregnancy test will only be performed in women with childbearing potential. It can be completed at Visit 1, 2 and/or 3 and Visit 7 or 8									
 Skin biopsy will be completed at either Visit 2 or 3.									
 NMR spectroscopy, clinical and research blood, and CPET testing can be performed at either Visit 2 or 3 for baseline timepoint and Visit 7 or 8 for end of treatment timepoint.									
* Procedure is optional (Echo is optional on Visit 1 if PI feels there is an adequate and timely historical Echo)									
Visits 1, 4, 5, 6, and 7 may take place at either WRNMMC or NIH Clinical Center.									
Visits 2, 3, 7B, 8, and 9 will take place at the NIH Clinical Center									

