### **Cardiopulmonary exercise testing:**

As the metabolic response to exercise indirectly reflect mitochondrial function, metabolic exercise testing will be conducted with 12-lead EKG monitoring after an overnight fast at baseline and at the end of 12 weeks of NR administration. Cardiopulmonary exercise testing will be performed using a ramp protocol while wearing a facemask enabling breath-by-breath analysis of inspired and expired air (SensorMedics, CA) as performed previously in our laboratory. EKGs are obtained at rest, after each minute of exercise, at end-exercise, and at each minute for 5 minutes after exercise. Blood pressure will be measured at rest, at the end of each stage of exercise (3 minutes in duration), at end-exercise, and at 3 minutes after exercise. Exercise will be symptom-limited (fatigue, shortness of breath or chest pain) and supervised by an experienced nurse and a LIP investigator of this study. Exercise will be terminated prior to this end-point if evidence of severe ischemia is noted ( $>2$  mm ST segment depression in leads with isoelectric segments at rest, hypotension, ventricular tachycardia) or if the patient wishes to stop exercise. For patients with interpretable EKGs (absence of significant resting ST-T wave or major conduction abnormalities), EKG criteria for ischemia is  $\geq 1$  mm ST segment depression with a horizontal or down-sloping configuration in at least 2 contiguous leads. Analysis of  $\text{VO}_{2\text{max}}$  and the anaerobic threshold will be measured and compared to each subject at baseline and after completion of the NR supplementation protocol. Subjects will be asked not to significantly modify activity levels for the duration of the 16-week study.

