## **7. Data and Biospecimen Management Plan**

### **Data Management and Access at the NIH:**

Primary research data will be coded by replacing individually identifying information (such as name) with a code that will enable the investigator to readily ascertain the identity of the subject through the use of a code-key, but will not reveal the identity of subjects to parties not authorized to have access to individual subject identifiers.

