## **8. Statistical Considerations**

#### ***Primary study outcome:***

Continuous data will be presented as mean  $\pm$  standard deviation or median and range, as appropriate. The primary outcome of this pilot study will be the comparison of baseline to 12-week (on NR) skeletal muscle fixed-load sub-maximal exercise NMR spectroscopy skeletal muscle phosphocreatine recovery time. We are proposing a novel study with no data available on the effect of NR on mitochondrial function as measured in-vivo as measured by NMR spectroscopy. However, we appeal to data in Wang, et. al (ref. 20) to aid with a preliminary sample size calculation. In the Wang, et. al. study, the mean recovery time in leg muscle

phosphocreatine levels after foot-exercise in the control group was  $36.7 \pm 6.6$  seconds. Based on the paired t-test, a sample of size 15 will allow our study to detect a 13% or greater relative reduction (4.8 sec or greater absolute reduction from 36.7 sec to 31.9 sec) in skeletal muscle recovery time with NR at 12 weeks compared to baseline with 80% power and a two-sided alpha of 0.05. The calculation assumes that the standard deviation of the recovery times of the paired baseline to 12-week differences on NR is the same as the standard deviation of the phosphocreatine recovery times in the control group (i.e. 6.6 sec) of the Wang, et. al. study. We request the enrollment of 20 subjects to allow for subject attrition and a margin of error for the study assumptions. The primary analysis of the primary endpoint will use a non-parametric Wilcoxon Signed Rank test for paired data.

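### The analyst who derives the primary phosphocreatine recovery time is not masked to visit, in an open-label single-arm study where visit and NR status are the same thing

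*Combined protocol and SAP*

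**What the plan says.** Section 3 states: "The study design is an open label pilot study with subjects serving as their own controls". Section 8 makes the change in phosphocreatine recovery time from baseline to 12 weeks on NR the primary outcome, tested with a Wilcoxon signed rank test.

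Section 5 (Skeletal muscle exercise NMR spectroscopy) fixes the rest, exercise and recovery periods and a single-exponential model. The time constant "is calculated with data obtained during the post-exercise recovery period", and "the results will be analyzed with the use of SAGE 7 (GE Healthcare) and IDL, version 6.4 (Exelis Visual Information Solutions), software". The section refers to a published NIH protocol. It does not say who processes the spectra, what that person knows about the visit, in what order scans are processed, or how a poor spectrum or fit is handled. A third scan follows at week 16 after washout; Section 8 gives it no analysis.

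For exercise testing, Section 5 says that "the anaerobic threshold will be measured and compared to each subject at baseline and after completion of the NR supplementation protocol". It names no masked reader and no rule for locating the threshold. Section 8 lists the threshold as an additional analysis.

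The nearest provision to masking is in Section 7: "Primary research data will be coded by replacing individually identifying information (such as name) with a code". That protects identity. It is not described as hiding the visit or the acquisition date.

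**The concern.** In a parallel-group trial, a reader who does not know the arm applies the same habits to both arms, and drift tends to cancel. Here there is no second arm. Anyone who knows that a scan is from week 12 knows that the subject was taking NR, and the stated hypothesis is directional: NR will improve muscle mitochondrial function. If processing or acceptance of fits differs even slightly by visit, the difference enters the paired change at full size and looks the same as an NR effect. More subjects do not dilute it; they make a false positive more likely.

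Subjects and treating staff cannot be masked in this design. The analyst can be, because the fit is made on stored spectra after acquisition.

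**Working it through.** **Inputs, all from Section 8:** 15 pairs; SD of paired differences 6.6 s (assumed there to equal the between-subject SD of an outside control group); planning mean 36.7 s; target reduction 4.8 s; two-sided alpha 0.05; power 80%.

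**The plan's own figure.** With the normal approximation, n = ((1.960 + 0.842) × 6.6 / 4.8)² = 14.84, so 15, and power at 15 is 80.4%. The stated sample size reproduces. (An exact paired t calculation gives 74.5% at n = 15; that is a separate matter.)

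**Smallest significant change.** The standard error is 6.6/√15 = 1.704 s and the critical t on 14 degrees of freedom is 2.145. A mean change of 2.145 × 1.704 = 3.65 s, or 10% of 36.7 s, reaches p = 0.05.

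**Effect of a systematic shift.** Set the true effect to zero and let each paired difference carry the same shift b from processing. The t statistic is then non-central t on 14 degrees of freedom with noncentrality b√15/6.6, and the false-positive rate is the probability that |t| exceeds 2.145. The documents give no figure for analyst variability, so b is an assumption throughout.

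| Assumed shift b | Share of 4.8 s target | Noncentrality | Paired t, n = 15 | Paired t, n = 20 |
|---|---|---|---|---|
| 0 s | 0% | 0 | 5.0% | 5.0% |
| 0.25 s | 5% | 0.147 | 5.2% | 5.3% |
| 0.5 s | 10% | 0.293 | 5.9% | 6.2% |
| 1 s | 21% | 0.587 | 8.5% | 9.9% |
| 2 s | 42% | 1.174 | 19.4% | 25.1% |

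For the planned Wilcoxon test at n = 15, simulation (40,000 runs, normal differences) gives 4.6% with no shift, 8.1% at 1 s and 18.5% at 2 s. The choice of test makes little difference.

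**What the table shows.** A shift of half a second or less hardly matters. A shift of 1 to 2 s, which is 2.7% to 5.4% of the planning mean, would matter. The same arithmetic holds for a 1 to 2 s bias from any source, so it measures vulnerability and is not evidence that the analyst introduces one.

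**The case against.** The strongest reply is that Section 5 leaves little to judgement. Exercise and recovery periods, model and software versions are fixed, and the work follows an established NIH protocol. No manual phasing, trimming or discarding of spectra is described. This stands to the extent that a reader might infer from the missing masking that analysts adjust spectra by hand; the documents do not say so. Nor do they say that processing is automated or give a rule for rejecting a fit. A statement that processing runs unattended with locked settings would largely answer the point for Tc.

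A second reply is that the study is an openly declared uncontrolled pilot, with larger threats that masking leaves untouched: time trend, learning, effort and regression to the mean. That is true. It limits what the change buys, but reader expectation is the one threat here that can be removed without a control group.

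A third concerns scope. A reader might infer that baseline against week 12 is the only contrast available, or that the echocardiograms are equally exposed. Neither follows. A week-16 washout scan is collected, although it has no stated analysis and its analyst is no better masked. Echo has no planned test in Section 8, and its baseline may be historical and from either of two sites, so masked reading by one person would mean re-reading studies. The echo should be left out of this point.

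**Conclusion.** The omission is clear: no section masks the analyst of the primary endpoint to visit, and visit determines NR status. That leaves a route by which processing or fit-rejection choices could add to the estimated effect with nothing in the design to separate them.

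The size is unknown. The illustrative false-positive rates run from about 5.2% at 0.25 s to about 19.4% at 2 s. They assume no true effect, 15 pairs, an SD of differences of 6.6 s, and the same shift in every subject. A reader might take the upper end as an expected inflation; the documents supply nothing from which to expect any particular shift, or any shift at all. The anaerobic threshold has the same gap, but it is an additional analysis and nothing is quantified for it.

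This is an inexpensive improvement to how the primary endpoint is read. It is not a finding that the result will be biased.

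**What to change.** Add to Section 5, Skeletal muscle exercise NMR spectroscopy, wording such as:

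> Acquisition quality is checked at each visit without deriving Tc. After a subject's last scan, the baseline, week-12 and week-16 spectra are stripped of visit label and date, given random codes by a team member who does not process them, and processed in random order by the analyst, masked to visit, with fixed processing settings. Acceptance or rejection of each fit is recorded before the codes are broken.

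The immediate quality check is needed because, under Section 3, NR starts on the evening after Visit 3. If all inspection waited for the last scan, an unusable baseline would be found only when it could no longer be repeated off treatment.

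The same recoding can be applied to stored breath-by-breath exercise-test files when the anaerobic threshold is read. The test itself is "supervised by an experienced nurse and a LIP investigator of this study" and stays unmasked, as does all real-time safety reading.

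The cost is a short protocol paragraph and a file-recoding step. No new reader, visit or procedure is needed, and the sample size and alpha do not change. The price is that Tc values become available only after each subject's last scan.
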